**Approval/Signature**

**CONFIDENTIAL**

This material is the property of Avid Radiopharmaceuticals, Inc. (Avid). The information is confidential and is to be used only in connection with matters authorized by Avid and no part of it is to be disclosed to others without prior written permission from Avid.

Sponsor: Avid Radiopharmaceuticals, Inc.	Name of Compound: Flortaucipir F 18 (  F-AV-1451)	Active Ingredient(s): 7-(6-[F-18]fluoropyridin-3-yl)-5H-pyrido[4,3-b]indole
Title of Study:  F-AV-1451-A23 A multicenter screening study with flortaucipir F 18 in patients with early symptomatic AD		
Planned number of subjects (Enrolled): Approximately 500		
Name of compound: flortaucipir F 18 (  F-AV-1451) Dose: 370 MBq (10 mCi) Route of Administration: Intravenous (IV) bolus		
Study Phase: II		
Study Centers: Approximately 15 centers in the United States and Canada		
Trial Objectives:  The primary objective of the protocol is: 
 
To pre-screen patients via a flortaucipir F 18 scan, who have objectively verified cognitive impairment and etiology diagnosed or suspected to be Alzheimer’s disease (AD), and have indicated their interest in participating in Lilly sponsored trials that require tau imaging for inclusion such as I5T-MC-AACG (AACG).
 
 The secondary objective of the protocol is: 
 
To expand the flortaucipir F 18 safety database.
 
		
Eligibility: See Section 5.3, Selection of Patients.		
Study Design:  Study  F-AV-1451-A23 is a multicenter screening study in patients with early symptomatic AD (where early symptomatic AD refers to the combination of 2 stages: prodromal AD [MCI-AD] and mild AD dementia).  All patients will provide informed consent before starting any study procedures. This pre-screening study targets patients who are interested in participating in AD therapeutic clinical trials and have expressed a preliminary interest in a trial like the AACG trial, and who are not known to meet any of the exclusion criteria for trials like AACG based on medical history and clinical examination. However, consent for this protocol does not constitute consent for the		

Sponsor: Avid Radiopharmaceuticals, Inc.	Name of Compound: Flortaucipir F 18 (  F-AV-1451)	Active Ingredient(s): 7-(6-[F-18]fluoropyridin-3-yl)-5H-pyrido[4,3-b]indole

AACG trial or any other trials, and subjects who qualify for this protocol may still fail to qualify for trials like AACG or other trials based on the results of this protocol or based on additional testing performed in those subsequent trials.
 
Screening assessments will include demographic information, cognitive testing, disease history, concomitant medications, vital signs, ECG and medical history. Patients who are deemed eligible to continue will complete a flortaucipir F 18 PET scan.
 
Patients who meet eligibility criteria will participate in this protocol until they have completed their flortaucipir F 18 PET scan, or they discontinue, withdraw consent, or if the sponsor decides to end this protocol early.
		

Details of the assessments that will be performed at each visit are detailed in Section 7.1. The following will be completed:
 
 
• Informed consent for patient;
 
• Demographics (age, gender, years of education, race, ethnicity); weight
 
• Medical history, concomitant medications;
 
• Vital Signs (pulse, respiratory rate, supine blood pressure);
 
• An ECG will be performed to assess the participant’s cardiac status. If an ECG was performed within the last 12 months of the flortaucipir (F) PET Imaging Visit and is available for review, the ECG does not need to be repeated.
 
• ApoE status, if available;
 
• Disease history (date/months since symptom onset, date/months since diagnosis, family history of relevant neurologic disease);
 
• Cognitive status interview, including MMSE;
 
• A physician will see the patient during the screening visit.
 
• For women of childbearing potential, a negative serum pregnancy test must be obtained at the screening visit
 
		

Statistical Methods:
 
Descriptive analyses will be applied to summarize patients’ demographic and baseline characteristics, and qualitative and quantitative assessments of the flortaucipir F 18 PET image.
		

## ABBREVIATIONS AND DEFINITIONS

Aβ	Beta amyloid
AChEI	Acetylcholinesterase inhibitor
AD	Alzheimer's disease
ADRs	Adverse Drug Reactions
Adverse Event (AE)	Any untoward medical occurrence in a subject or clinical investigation subject administered a pharmaceutical product and that does not necessarily have a causal relationship with this treatment.
Audit	A systematic and independent examination of the trial-related activities and documents to determine whether the evaluated trial-related activities were conducted, and the data were recorded, analyzed, and accurately reported according to the protocol, applicable standard operating procedures (SOPs), good clinical practice (GCP), and the applicable regulatory requirement(s).
Case Report Form (CRF) and electronic Case Report Form (eCRF)	A printed or electronic form for recording study participants' data during a clinical study, as required by the protocol.
CNS	Central Nervous System
CRO	Contract Research Organization: A person or organization (commercial, academic, or other) contracted by the sponsor to perform one or more of the sponsor's trial-related duties and functions.
ECG	Electrocardiogram
EMA	European Medicines Agency
FDA	US Food and Drug Administration
FDG	 F – Fluorodeoxyglucose
GCP	Good Clinical Practice
IB	Investigator's Brochure
ICF	Informed Consent Form

ICH	International Conference on Harmonization
IHC	Immunohistochemistry
IND	Investigational New Drug
Institutional Review Board /Independent Ethics Committee	A board or committee (institutional, regional, or national) composed of medical and nonmedical members whose responsibility is to verify that the safety, welfare and human rights of the subjects participating in a clinical study are protected.
Investigator	A person responsible for the conduct of the clinical trial at a trial site. If a trial is conducted by a team of individuals at a trial site, the investigator is the responsible leader of the team and may be called the principal investigator.
IV	Intravenous
Kd	Dissociation Constant
keV	Kiloelectron volt
LAR	Legally Authorized Representative
MBq	Megabecquerel
mCi	Millicurie
MCI	Mild Cognitive Impairment
MHD	Maximum Human Dose
MMSE	Mini Mental Status Exam
MRI	Magnetic Resonance Imaging
mSv	Millisievert
NDA	New Drug Application
nM	Nanometer
NOAEL	No Observable Adverse Effect Level
PET	Positron Emission Tomography
PhRMA	Pharmaceutical Research and Manufacturers of America

**SAE**                      Serious Adverse Event

**SOP**                      Standard Operating Procedures

## 1. INTRODUCTION

Molecular imaging biomarkers have the potential to aid in the diagnosis of patients with cognitive impairment who are being evaluated for Alzheimer's disease (AD) (Dubois, 2010; McKhann, 2011). Positron emission tomography (PET) ligands such as florbetapir F 18 (Wong, 2010) may provide a minimally invasive estimate of cortical beta amyloid (A $\beta$ ) neuritic plaque deposition, a hallmark pathology, and a required element for the evaluation of AD neuropathologic diagnosis (Hyman 2012). Multiple studies comparing amyloid PET scans to histopathologic assessment of amyloid burden, in subjects for whom biopsy samples were available or who came to autopsy after receiving a PET amyloid scan, support the relationship between PET amyloid imaging results and cortical neuritic plaque density (Clark 2011, 2012; Leinonen, 2008; Sojkova, 2011; Kantarci, 2011; Burack, 2010). The largest of these studies (Clark 2012) demonstrated a high sensitivity and specificity for florbetapir PET to discriminate subjects with subsequent autopsy findings of no or sparse neuritic plaques (amyloid negative) from those with moderate to frequent plaques (amyloid positive).

The ability to image brain amyloid with compounds such as florbetapir is an important advance for diagnosis of neurological disease. An amyloid negative florbetapir PET scan indicates the absence of a hallmark pathology and is inconsistent with a diagnosis of AD. However, because amyloid is believed to accumulate very early in the disease process (Jack et al., 2010) and may be present in other diseases or in clinically normal elderly subjects (Sperling et al. 2011; Price and Morris, 1999), the density or distribution of amyloid in subjects with a positive scan is not associated with Alzheimer's disease severity, has not been established to predict rate of future deterioration and has not been established as a tool to predict or monitor response to therapy.

In contrast to A $\beta$  neuritic plaques, the density and distribution of phosphorylated tau, aggregated in neurofibrillary tangles, increases with AD-related cognitive impairment and correlates with neurodegeneration (Dickson et al., 1997; Duyckaerts et al., 1987). Thus, a PET imaging agent that binds to phosphorylated tau has potential application as a biomarker for disease severity/neurodegeneration and may be useful both for selecting patients for therapy and for monitoring disease progression in therapeutic trials.

Flortaucipir F 18 (F-AV-1451) (originally named [F-18]T807 by Siemens Molecular Imaging Biomarker Research group) has been developed as a positron emitting radiopharmaceutical for *in vivo* imaging of tau protein aggregates (Xia et al., 2013). Autoradiography results using tissue sections from human brains showed a strong signal in the grey matter of cortical slices from tau positive brains but weak or no binding in tau negative, A $\beta$  positive, or tau and A $\beta$  negative tissue. Scatchard analysis based on this heterogeneous autoradiography assay yielded an estimated Kd of 15nM. A saturation binding experiment using purified Paired Helical Fragment Tau isolated brains of AD patients yielded a Kd value of 0.54 nM.

An updated summary of preclinical and clinical experience pertaining to the safety of flortaucipir (F) can be found in the investigator's Brochure. Briefly, preclinical toxicity studies of 19F-AV-1451 (non-radioactive flortaucipir (F), "AV-1451") showed a good safety profile with no observable effects at high multiples of the intended maximum

human dose. AV-1451 was positive in the in vitro hERG assay. However, the cardiovascular assessments performed during the dog toxicology studies showed no evidence that AV-1451 prolongs the QT interval at high multiples of relevant clinical doses, and therefore the risk of QT prolongation is not included in the risk profile.

Human dosimetry results for flortaucipir (F) showed both hepatobiliary and renal excretion, and total effective dose similar to other approved F-18 radiopharmaceuticals. The organs of the gastrointestinal tract (upper large intestine, small intestine, and liver) received the greatest exposure. The whole body effective dose for a 10 mCi (370 MBq) dose of flortaucipir (F) was calculated to be 8.70 mSv. In human clinical studies so far, flortaucipir (F) is generally well-tolerated with a low incidence of mild and transient adverse events.

Image assessment showed tracer deposition on brain PET scans to be consistent with that expected for a tracer of aggregated tau protein. Flortaucipir (F) initially entered the brain and was subsequently eliminated from the brain in clinically normal and amyloid negative cognitively impaired subjects, yielding only a diffuse pattern of background activity, whereas a regionally distinct gray matter distribution of increased tracer retention was observed in amyloid positive cognitively impaired subjects (Pontecorvo et al., 2017). Preliminary analyses of our Phase II longitudinal study (A05, exploratory cohort) also indicate a relationship between the level and pattern of flortaucipir uptake at baseline, and the rate of decline on cognitive tests over an 18 month period (Mintun, AAIC 2017). These results suggest that it may be possible to use flortaucipir PET scans to enrich clinical studies for subjects with a desired level of AD pathology and a more homogeneous rate of cognitive decline, thus increasing power to detect a treatment effect. Specifically, Lilly and Avid desire to conduct treatment trials at the earliest stage of AD neuropathology to maximize potential patient benefit.

AACG is a proposed anti-amyloid trial that intends to target patients with a certain distribution and density of tau neurofibrillary tangles that are hypothesized to be appropriate for such a trial. It is thought that patients with no tau will progress so slowly that a clinical treatment effect could not be discerned, and those with a large tau burden may not be responsive to anti-amyloid therapy as their cognitive impairment is driven primarily by tau pathology. The overarching goal of this protocol is to test this hypothesis by pre-screening patients with flortaucipir F 18 who have been diagnosed with suspected Alzheimer's disease and have indicated their interest to consider participation in trials such as the AACG Lilly therapeutic clinical trial.

## **2. STUDY OBJECTIVES**

[figure not shown]
The primary objective is to pre-screen patients via a flortaucipir F 18 scan, who have objectively verified cognitive impairment and etiology diagnosed or suspected to be Alzheimer's disease, and have indicated their interest in participating in Lilly sponsored trials that require tau imaging for inclusion such as I5T-MC-AACG (AACG).

The secondary objective of the study is to expand the flortaucipir F 18 safety database.

## 4. TEST DRUG AND CONTROL AGENTS

### 4.1. Descriptive Name: F AV-1451

7-(6-[F-18]fluoropyridin-3-yl)-5H-pyrido[4,3-b]indole

MW = 262.27 amu

### 4.2. Radioactive Labeling

The compounds are labeled with [F] fluorine that decays by positron ( $\beta^+$ ) emission and has a half-life of 109.77 min. The principal photons useful for diagnostic imaging are the 511 keV gamma photons, resulting from the interaction of the emitted positron with an electron.

### 4.3. Decay Characteristics

The time course of radioactive decay for Fluorine [F] is shown below

Min.	Fraction Remaining
0	1.000
30	0.827
60	0.685
90	0.567
120	0.469
150	0.388
180	0.321
210	0.266
240	0.220

Physical decay chart for Fluorine [F]. Half-life = 109.77 min.

### 4.4. Packaging flortaucipir F 18 Injection

Each package of flortaucipir F 18 Injection includes a sterile apyrogenic sealed glass vial or sterile apyrogenic syringe containing flortaucipir F 18 Injection, a surrounding protective lead shield canister, and an outside delivery case.

### 4.5. Storage and Handling flortaucipir F 18 Injection

Flortaucipir F 18 Injection is stored at room temperature. Flortaucipir F 18 Injection should be stored within the original container or equivalent radiation shielding.

## **5. INVESTIGATIONAL PLAN**

### **5.1. Overall Design and Plan of the Study**

Study F-AV-1451-A23 is a multicenter screening study in patients with early symptomatic AD (where early symptomatic AD refers to the combination of 2 stages: prodromal AD [MCI-AD] and mild AD dementia).

All patients will provide informed consent before starting any study procedures. This pre-screening study targets patients who are interested in participating in AD therapeutic clinical trials and have expressed a preliminary interest in a trial like the AACG trial, and who are not known to meet any of the exclusion criteria for trials like AACG based on medical history and clinical examination. However, consent for this protocol does not constitute consent for the AACG trial or any other trials, and subjects who qualify for this protocol may still fail to qualify for trials like AACG or other trials based on the results of this protocol or based on additional testing performed in those subsequent trials.

Screening assessments will include demographic information, cognitive testing, disease history, concomitant medications, vital signs, ECG and medical history. Patients who are deemed eligible to continue will complete a flortaucipir F 18 PET scan.

Patients who meet eligibility criteria will participate in this protocol until they have completed their flortaucipir F 18 PET scan, or they discontinue, withdraw consent, or if the sponsor decides to end this protocol early.

### **5.2. Planned Dosage and Duration of Treatment**

#### **5.2.1. Flortaucipir F 18 Dosage and Administration**

All subjects will receive a single IV bolus administration target dose of 370 MBq (10 mCi) of flortaucipir F 18 Injection.

#### **5.2.2. Rationale for Dosages**

Flortaucipir F 18 will be administered IV in a radioactive dose of 370 MBq (10mCi) with a maximum human dose (MHD) limited to 20 µg of compound by weight. This dose is 150 fold lower than the NOAEL observed in the rat single dose toxicity study and is 50 fold lower than the NOAEL observed in the rat and dog repeat dose toxicity studies.

Human dosimetry has been obtained in nine subjects. The results estimated an Effective Dose of 8.70 mSv for an anticipated 370 MBq (10 mCi) injection and is comparable to the effective dose of approved F-labeled compounds such as FDG and florbetapir F 18 injection.

The proposed dose has been shown to have acceptable image quality in previous human studies. No treatment related adverse events have been reported using this regimen.

### **5.3. Selection of Subjects**

#### **5.3.1. Inclusion Criteria**

Patients must meet the following criteria to enroll in this study:

1. Men or women, at least 60 to 85 years of age at the time of consent;
2. Patients with gradual and progressive change in memory function for  $\geq 6$  months;
3. Patients who have a Mini Mental State Examination (MMSE) score between 20-27 inclusive;
4. Patients who are willing to undergo a PET scan using flortaucipir F 18;
5. Patients who give informed consent or have a legally authorized representative (LAR) to consent for enrollment; and

#### **5.3.2. Exclusion Criteria**

Patients who meet any of the following criteria are not eligible to enroll:

1. Patients who lack, in the investigator's opinion, adequate premorbid literacy, adequate vision, or adequate hearing to complete the required psychometric testing;
2. Are females of childbearing potential who are not surgically sterile, not refraining from sexual activity or not using reliable methods of contraception. Females of childbearing potential must not be pregnant (negative serum  $\beta$ -HCG at screening and negative urine  $\beta$ -HCG prior to flortaucipir F 18 injection) or breastfeeding at screening. Females should agree to avoid becoming pregnant by refraining from sexual activity or using reliable contraceptive methods for 24 hours following administration of flortaucipir F 18 injection;
3. Have significant neurological disease affecting the CNS, other than AD, that may affect cognition or ability to complete the study, including but not limited to, other dementias, serious infection of the brain, Parkinson's disease, multiple concussions, or epilepsy or recurrent seizures (except febrile childhood seizures);
4. Patients with any current primary psychiatric diagnosis other than AD if, in the judgment of the investigator, the psychiatric disorder or symptom is likely to confound interpretation of drug effect, affect cognitive assessment, or affect the patient's ability to complete the study [Patients with history of schizophrenia or other chronic psychosis are excluded.];
5. Intend to use drugs known to significantly prolong the QT interval within 14 days or 5 half-lives, whichever is longer, of a scheduled screening/baseline flortaucipir F 18 PET scan, or have medical history of risk factors for Torsades de Pointes.
6. Have an average ECG corrected QT (QTcF) interval measurement  $>450$  msec (men) or  $>470$  msec (women) at screening (as determined at the investigational site).

7. Have ocular pathology that significantly limits ability to reliably evaluate vision or the retina;
8. Have a history of alcohol or drug disorder (except tobacco use disorder) within 2 years before the screening visit;
9. Have a current serious or unstable illnesses including retinal, cardiovascular, hepatic, renal, gastroenterologic, respiratory, endocrinologic, neurologic (other than AD), psychiatric, immunologic, or hematologic disease and other conditions that, in the investigator's opinion, could interfere with the analyses in this study; or has a life expectancy of <24 months;
10. Has a history of cancer within the last 5 years, with the exception of non-metastatic basal and/or squamous cell carcinoma of the skin, in situ cervical cancer, non-progressive prostate cancer, or other cancers with low risk of recurrence or spread;
11. Patients with a past history (suspected or confirmed) of Hepatitis B or Hepatitis C;
12. History of vitiligo and/or current evidence of post-inflammatory hypopigmentation;
13. Have had prior treatment with a passive anti-amyloid immunotherapy <5 half-lives prior to randomization;
14. Have previously participated in any other study investigating active immunization against A $\beta$ ;
15. Patients that are currently enrolled in any other interventional clinical trial involving an investigational product or any other type of medical research judged not to be scientifically or medically compatible with this study
16. Contraindication to PET;
17. Has hypersensitivity to flortaucipir F 18 or any of its excipients;
18. Present or planned exposure to ionizing radiation that, in combination with the planned administration of study PET ligands, would result in a cumulative exposure that exceeds local recommended exposure limits;
19. Has previous MRI evidence of significant abnormality that would suggest another potential etiology for progressive dementia or a clinically significant finding that may impact the patient's ability to safely participate in the study;
20. Have any contraindications for MRI, including claustrophobia or the presence of contraindicated metal (ferromagnetic) implants/cardiac pacemaker;
21. Have poor venous access;
22. Are investigator site personnel directly affiliated with this study and/or their immediate families; immediate family is defined as spouse, parent, child, or sibling whether biological or legally adopted;

23. Are Lilly employees or are employees of third-party organizations (TPOs) involved in a study that requires exclusion of their employees;
24. In the opinion of the investigator, are otherwise unsuitable for a study of this type.

#### **Prior/Concomitant Therapy**

25. Have received treatment with a stable dose of an acetylcholinesterase inhibitor (AChEI) and/or memantine for less than 2 months before randomization [If a patient has recently stopped an AChEI and/or memantine, he or she must have discontinued treatment at least 2 months before randomization.].
26. Current use of strong inducers of CYP3A;
27. Are currently on medication(s) known to significantly prolong the QT interval;
28. Have allergies to either monoclonal antibodies, diphenhydramine, epinephrine, or methylprednisolone;
29. Have known allergies to LY3002813, related compounds, or any components of the formulation; or history of significant atopy;
30. Have known allergies to LY3202626, related compounds, or any components of the formulation;
31. Changes in concomitant medications that could potentially affect cognition and their dosing should be stable for at least 1 month before screening, and between screening and randomization (does not apply to medications discontinued due to exclusions or with limited duration of use, such as antibiotics).

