#### **8.1.1. Population for Analysis**

The safety analysis population will include all eligible patients who enroll in F-AV-1451-A23 (A23) and have received at least one dose of flortaucipir F 18 injection. Efficacy analysis population will include all subjects in safety population, and with a valid flortaucipir F 18 scan assessment (quantitative and/or qualitative).

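### The safety population admits only eligible dosed subjects, and three of the criteria that decide eligibility count from a randomization that A23 does not contain

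*Protocol*

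**What the plan says.** **Populations.** Protocol 8.1.1 begins: "The safety analysis population will include all eligible patients who enroll in" the study, and then adds receipt of at least one dose. SAP 8.1.2 repeats this and assigns all demographic, baseline and safety endpoints to that population. The efficacy population in Protocol 8.1.1 and SAP 8.1.3 is the part of the safety population with a valid scan assessment. SAP 8.3 lists subjects who entered without satisfying the entry criteria. It does not say how they are treated in the tables.

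**Objective.** Protocol 2 states: "The secondary objective of the study is to expand the flortaucipir F 18 safety database".

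**Criteria.** Protocol 5.3.2 makes a patient who meets any exclusion criterion ineligible to enroll. Three of the 31 criteria use randomization as their time reference:

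- Criterion 13: "Have had prior treatment with a passive anti-amyloid immunotherapy <5 half-lives prior to randomization".
- Criterion 25, first limb: "Have received treatment with a stable dose of an acetylcholinesterase inhibitor (AChEI) and/or memantine for less than 2 months before randomization". Second limb, for patients who recently stopped: "he or she must have discontinued treatment at least 2 months before randomization".
- Criterion 31, on medications that could affect cognition: "should be stable for at least 1 month before screening, and between screening and randomization". Only the second limb depends on randomization.

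Criterion 5, by contrast, is tied to an event that A23 does contain: "whichever is longer, of a scheduled screening/baseline flortaucipir F 18 PET scan".

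**Design.** Every subject receives the same single injection (SAP 4.3, 4.4) and is summarized in one group (SAP 7.1). Protocol 5.1 keeps A23 separate from any later trial: "subjects who qualify for this protocol may still fail to qualify for trials like AACG or other trials based on the results of this protocol".

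**The concern.** A safety population is normally everyone exposed. Here a second condition, eligibility, is added. A subject who was injected but turns out to have breached a criterion would then leave the adverse event tables of a study whose secondary objective is to add exposed subjects to a safety database. The same subject would leave the baseline and scan tables. This holds for any of the entry criteria.

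Criteria 13, 25 and the second limb of 31 make it sharper. For most criteria one can at least establish whether a breach occurred. For these three the reference date lies outside A23, is unknown at enrolment and may never exist. A subject's place in the tables would rest on a condition that the A23 data cannot settle.

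**Working it through.** There is no plan figure to reproduce. The documents give no statistical derivation of the approximately 500 subjects, and the point does not depend on one. The check is of text and logic, with two small calculations.

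**1. Is there a randomization in A23?** The word occurs four times in the eligibility criteria: once in 13, twice in 25 and once in 31. The schedules in Protocol 11.2 and SAP 6.1 contain screening, imaging, end of imaging and a follow-up call. No allocation step appears, and neither document says that the word refers to another trial.

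**2. Does the missing date change anyone's status?** For criterion 25, let d be the days on a stable dose (or since stopping) at the scan, and L the days from the scan to some later randomization, with no change in between. Take 2 months as 61 days. The patient is excluded if d + L < 61. Both d and L are assumed values.

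| d | L = 0 | L = 14 | L = 30 | L = 60 | L = 90 |
|---|---|---|---|---|---|
| 30 | excluded (30) | excluded (44) | excluded (60) | not (90) | not (120) |
| 45 | excluded (45) | excluded (59) | not (75) | not (105) | not (135) |
| 59 | excluded (59) | not (73) | not (89) | not (119) | not (149) |
| 61 | not (61) | not (75) | not (91) | not (121) | not (151) |

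Below about 2 months the answer depends on L, which A23 does not record. From 61 days the patient passes whatever L is, so the difficulty is confined to recently treated patients. Criterion 13 has the same structure with a window of five half-lives. The second limb of criterion 31 covers an interval whose end point is not in the A23 schedule, so it cannot be completed within A23.

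**3. Where does eligibility enter the analysis?** Eligible and dosed gives the safety population (Protocol 8.1.1, SAP 8.1.2). Adding a valid scan assessment gives the efficacy population (SAP 8.1.3). The restriction therefore reaches every adverse event, baseline and imaging table.

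**4. How large could the effect be?** The documents do not give the number affected. For scale only, assume 500 dosed subjects (500 is the planned enrolment, so the dosed number may be lower).

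- One subject left out who had the only serious treatment-emergent event: 1/500 = 0.20% (exact 95% CI 0.005% to 1.11%) becomes 0/499 = 0% (0% to 0.74%).
- With no events of a given type, the one-sided 95% upper bound is 1 − 0.05^(1/n). For n = 500 it is 0.597%. If an assumed 1%, 5% or 10% of subjects are left out, n = 495, 475 or 450 and the bound is 0.603%, 0.629% or 0.664%.

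Precision hardly moves. What could change visibly is whether a rare event appears in a table.

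**The case against.** **Randomization plainly means randomization in a later trial such as AACG.** This is the likely reading. A23 targets patients not known to meet exclusion criteria for such trials, criteria 28 to 30 suit a therapeutic trial, and criterion 31 places randomization after screening. It explains the wording but does not supply a date when A23 eligibility is decided.

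**Eligible can be read as accepted at entry, so no dosed subject would be dropped.** This is a fair reading, and the sponsor may well proceed that way. But SAP 8.3 expects some subjects to enter without satisfying the criteria, and the literal population definition then leaves them out.

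**Nobody would disappear from the report.** This largely stands. The disposition table covers all enrolled subjects and includes the analysis populations (SAP 8.2). All adverse events and all eCRF data are listed (SAP 8.11.2, 7.1). Protocol 8.2 also says that all subjects with serious adverse events or discontinuing for adverse events are summarized, with no eligibility limit. SAP 8.1.2 nonetheless ties the safety tables to the restricted population.

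**Two stronger inferences are tempting and are not supported.** A reader might infer that population membership depends on the scan result, since entry to a later trial depends partly on it. No passage re-judges A23 eligibility with later-trial data. A reader might also infer a sizeable loss of subjects. Under the likely reading, someone never randomized cannot breach these limbs. If the later trial applies the same limits (an assumption, since that protocol is not available here), someone in breach would not be randomized. The number lost would then be close to zero.

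**Conclusion.** The point holds as a flaw in the population definition, made sharper by three criteria with no reference date in A23. As written, both documents allow exposed subjects to be left out of the safety tables, which works against the secondary objective.

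Its size is modest. The number affected is not stated and is probably small, every analysis is descriptive, and no test, power or inferential result changes. The illustrations rest on an assumed 500 dosed subjects and assumed numbers left out. It is worth correcting because the correction is cheap and removes the dependence altogether.

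A minor and separate gap lies in SAP 8.10.1 and 8.10.2, which split scan results by subject eligibility without saying which eligibility is meant. If it is A23 eligibility, the current efficacy population contains only eligible subjects and the split has one level. If it is eligibility for a later trial, the criteria and data source are not given. This does not depend on criteria 13, 25 and 31.

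**What to change.** 1. In Protocol 8.1.1 and SAP 8.1.2, define the safety population as all subjects who received flortaucipir F 18, deleting the word eligible. Keep ineligible dosed subjects in the SAP 8.3 listing. The safety and overall scan tables then no longer depend on any eligibility ruling. If only the SAP is changed, record the difference in SAP 5.2.
2. Reconcile criteria 13, 25 and 31 with the A23 schedule, so that each can be judged when eligibility is decided. The reference event and the windows are for the sponsor to choose.
3. Separately, state in SAP 8.10.1 and 8.10.2 which protocol's eligibility is meant, from which data, and fixed at what time.

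The cost is one word in each document, amendment wording for three criteria and one SAP definition. The first change needs no new data or visits. The third may need a named outside data source if later-trial eligibility is intended, because the A23 schedule shows no assessment that records it.
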